11.10 Publication and Dissemination policy	60
12. REFERENCES	62
SIGNATURE PAGE 1 (Chief Investigator)	64
SIGNATURE PAGE 2 (Sponsor)	65

Short Title:	Protocol No:	Sponsor:	Version: 5.0
IP4 - CHRONOS	19CX5006	Imperial College London	Date:
			13 th July 2022

SIGNATURE PAGE 3 (Statistician)66	
SIGNATURE PAGE 4 (Principal Investigator)67	

TRIAL SUMMARY

TITLE	Comparative Health Research Outcomes of NOvel Surgery in prostate cancer			
AIM	To deliver an overarching RCT framework to efficiently evaluate novel surgical techniques in the treatment of non-metastatic prostate cancer			
	CHRONOS-A Pilot: To determine if men will agree to participate in an RCT that randomly assigns them to focal therapy alone or radical therapy (radiotherapy or prostatectomy).			
	Main: To determine if focal therapy alone is non-inferior when compared to radical therapy (radiotherapy or surgery) in terms of progression-free survival (PFS) at 5 years in men with clinically significant non-metastatic cancer.			
	CHRONOS-B Pilot: To determine if men expressing a preference for focal therapy will agree to participate in a multi-arm, multi-stage (MAMS) RCT that randomly assigns them to focal therapy alone or focal therapy in combination with neoadjuvant and/or adjuvant agents.			
	Main: To determine if focal therapy combined with neoadjuvant and/or adjuvant agents, compared to focal therapy alone, will improve failure-free survival (FFS) at 5 years, in men with clinically significant non-metastatic cancer			
PHASE	Phase II Randomised Control Trial (RCT) incorporating an internal pilot			
DURATION	Pilot: Recruitment 12 months. Minimum 3 months follow-up. Total 15 months. Main study: Recruitment further 48 months. Total including follow-up = 96 months			
DESIGN	Randomised controlled trial Two linked RCTs with CHRONOS-A and CHRONOS-B discussed with patients and choice of A or B dependent on physician and patient equipoise.			
	- CHRONOS-A Two arm RCT			
	- CHRONOS-B Multi-Arm Multi-Stage (MAMS) Randomised Control Trial			

Short Title: IP4 - CHRONOS	Protocol No: 19CX5006	Sponsor: Imperial College London	Version: 5.0 Date: 13 th July 2022
			10 daily 2022

SAMPLE SIZE	Eggeihility/nilot		
SAIVIPLE SIZE	Feasibility/pilot		
	CHRONOS-A 60 patients over 12-months (These participants will form part of the main study if feasibility is met and funding obtained)		
	CHRONOS-B 60 patients over 12-months (These participants will form part of the main study if feasibility is met and funding obtained)		
	Main study		
	CHRONOS-A 1190 patients		
	CHRONOS-B A three-arm MAMS RCT would require 1260 patients		
FEASIBILITY AND PILOT STUDY OBJECTIVES	To assess the feasibility of a trials framework that fits with existing patient and physician equipoise so that we can successfully and efficiently answer the next generation of research questions to evaluate medium-term outcomes following minimally invasive focal therapy in the treatment of clinically significant, non-metastatic prostate cancer.		
	 The embedded internal pilot objectives are: To determine patient acceptance to randomisation. To conduct an embedded qualitative study of patient and clinician acceptance and experience of the linked RCT CHRONOS design. To establish the feasibility of an economic evaluation alongside the main trial. To determine acceptability and completeness of resource use and utility measures (EQ-5D-5L). To identify the relevant NHS and non-NHS resource use to be collected alongside the main trial. To identify the relevant items to populate the Cost and Consequences framework. To perform preliminary analysis of pattern of missing data. 		
MAIN STUDY PRIMARY OBJECTIVES	CHRONOS-A To evaluate PFS rates of focal therapy alone compared to radical therapy (radiotherapy or surgery) in the treatment of non-metastatic clinically significant prostate cancer.		
	CHRONOS-B To evaluate FFS rates of focal therapy alone compared to focal therapy combined with other therapies as a neoadjuvant and/or adjuvant strategy.		
MAIN STUDY SECONDARY OBJECTIVES	Disease control Determine the histological, biochemical and oncological disease control for men undergoing radical therapy, focal therapy or focal therapy with neo/adjuvant treatments.		
	Adverse events and Functional Outcomes Determine the adverse events and functional outcomes after radical therapy, focal therapy or focal therapy with neo/adjuvant treatments		
	Health economics		

Short Title: IP4 - CHRONOS	Protocol No: 19CX5006	Sponsor: Imperial College London	Version: 5.0 Date: 13 th July 2022
-------------------------------	--------------------------	-------------------------------------	---

- To establish the NHS costs of the different interventions.
- To determine the Cost per QALYs (CUA), cost per PFS/FFS (CEA) and cost and consequences (CCA).
- To determine acceptability and completeness of resource use and utility measures (EQ-5D-5L).

Qualitative

- Patient experience of consent and recruitment, including reasons for declining participation.
- Participants' motivation to accept randomisation to and compliance with an intervention, which may or may not include neoadjuvant and adjuvant treatments.
- Patients' understanding and experience of each trial arm.
- Patients' experience of toxicities, focusing on erectile dysfunction and urinary symptoms.
- Patients' attitudes to the predicted survival rate.
- Potential improvements to recruitment processes.
- Healthcare professionals' attitudes to intervention arms and trial design and whether this might impact on recruitment.

Biobank and databank objectives

- To evaluate cancer infiltrating immune cells and immune gene signatures following ablation.
- To build a biobank and databank of matched imaging, blood, serum, plasma and pre-digital rectal examination urine as well as FFPE biopsy samples.

ELIGIBILITY CRITERIA

Inclusion

- Histologically confirmed prostate adenocarcinoma.
- PSA </=20ng/ml.
- Patients must have undergone a diagnostic pre-biopsy MRI compliant with national uro-radiology consensus guidelines. Dynamic contrast enhancement using gadolinium is not required at diagnostic stage. However, contrast enhancement MRI will be required in those men who undergo focal therapy prior to focal therapy as a baseline for comparison during follow-up. In the absence of a compliant diagnostic MRI (for clinical or other reasons), a transperineal template mapping biopsy using a 5-10 mm sampling frame will be required.
- Overall Gleason score of 7 (either 3+4=7 or 4+3=7) of any length or Gleason 3+3=6 provided >/=6mm cancer core length in any one core. Patients with Gleason 4+4=8 in some cores but where the overall Gleason score is 7 will be included.
- Patients with bilateral histologically proven prostate cancer are permissible provided the following criteria are met:
 - The index lesion to be treated, if focal therapy is used, meets the above histological criteria.
 - The patient may have a PIRADS or Likert score 3, 4, 5 mpMRI lesion in the same hemi-gland (either right/left or anterior/posterior) as the histological index lesion.
 - Secondary areas of Gleason 3+3=6 of </=5mm cancer outside of the treatment field can be monitored, if present, and the patient undergoes focal therapy.
 - If a Likert or PIRADS score 3,4 or 5 mpMRI lesion is present in an area outside of the treatment field, with a negative biopsy for cancer, then pathology must be reviewed with confirmation of the presence of inflammation or atrophy, if the patient is to undergo focal therapy*.
- Radiological stage T2b/T3a will require central review regarding suitability for focal therapy.

Short Title: IP4 - CHRONOS	Protocol No: 19CX5006	Sponsor: Imperial College London	Version: 5.0 Date: 13 th July 2022
			10 0diy 2022

- Index tumour volume, as seen on mpMRI if carried out, will be restricted to 50% of one lobe for either unilateral or bilateral ablation. Patients with tumour volume >/=50% of one lobe will require central review prior to enrolment. Final decisions on suitability of focal therapy will lie with the trial central review in these cases**.
- Age at least 18 years of age.
- Participants must be fit to undergo all procedures listed in the protocol as judged by clinical team.

*A biopsy of a suspicious mpMRI area may miss underlying cancer due to targeting error. However, if there is an alternative diagnosis for the changes on mpMRI such as inflammation or atrophy then this risk is reduced.

**This is to ensure that inappropriately large tumours are not being treated with focal therapy.

Exclusions

- Previous or current LHRH agonist or LHRH antagonist or anti-androgen use in CHRONOS-B.
- Patients already established on a 5 alpha-reductase inhibitor (finasteride or dutasteride) who wish to go into CHRONOS-B will need to discontinue this for at least 6 months prior to randomisation. (NB: testosterone supplementation is permitted).
- Previous treatment for prostate cancer.
- Life expectancy likely to be less than 10 years.
- Unable to give informed consent.

STUDY PROCEDURES

CHRONOS-A

- Arm 1 (Control): Radical therapy (radiotherapy or prostatectomy [radiotherapy can be external beam or brachytherapy]). In patients undergoing radiotherapy a maximum of 6-months neo-adjuvant hormonal therapy will be allowed. In patients undergoing radical prostatectomy, cytoreduction of maximum 6 months with medication will be permissible, provided this is part of local practice.
- Arm 2 (Intervention): Focal therapy alone (high intensity focused ultrasound [HIFU] or cryotherapy as per physician and centre choice). A second focal therapy session in-field, or a first focal therapy session to an out-of-field progressive or de novo lesion will be allowed as part of the focal therapy intervention.

CHRONOS-B

- Arm 1 (Control): Focal therapy alone (high intensity focused ultrasound [HIFU] or cryotherapy as per physician and centre choice). A second treatment infield, or a first focal ablation to an out-of-field progressive or de novo lesion will be allowed but will be regarded as failure events for the purpose of CHRONOS-B.
- Arm 2 (Intervention): Neoadjuvant finasteride 5mg once daily for a minimum of 12 weeks followed by focal therapy (as per control arm).
- Arm 3 (Intervention): Neoadjuvant bicalutamide 50mg once daily therapy for a minimum of 12 weeks followed by focal therapy (as per control arm). Other arms can be added in future with protocol amendments.

Protocol No:	Sponsor:	Version: 5.0
19CX5006	imperial College London	Date:
		13 th July 2022
	Protocol No: 19CX5006	

FEASIBILITY	CHRONOS-A and CHRONOS-B Pilot Outcome Measures		
AND PILOT STUDY	Primary		
ENDPOINTS	Feasibility and acceptance of randomisation (rate per -month, per -centre)		
	averaged) and compliance to allocated arm.		
	Secondary Patients' experience of concept and regruitment, including reasons for		
	 Patients' experience of consent and recruitment, including reasons for declining participation. 		
	Patients' motivation to accept randomisation to, and compliance with an		
	intervention and understanding of each trial arm.		
	Patients' experience of each arm including systemic issues, erectile dysfunction, urinary symptoms and rectal symptoms.		
	Healthcare professionals' attitudes to intervention arms and trial design		
	and whether this might impact on recruitment.		
	Proportion of patients successfully recruited into each of CHRONOS-A and		
	CHRONOS-B		
	 Potential improvements to recruitment processes. To establish the feasibility of an economic evaluation alongside the main 		
	trial.		
PRIMARY	CHRONOS-A: Progression-Free survival (PFS) defined as biochemical failure		
ENDPOINTS	(radical therapies only) or salvage therapy (local or systemic) or prostate cancer		
(Main Stage)	metastases or prostate cancer specific mortality.		
	CHRONOS-B: Failure-Free survival (FFS) defined as more than one focal therapy		
	session or salvage therapy (local or systemic) or prostate cancer metastases or		
OFCONDARY	prostate cancer specific mortality.		
SECONDARY ENDPOINTS	Disease control Rates of positive biopsy for any prostate cancer and significant cancer		
(Main Stage)	defined by a number of different thresholds on biopsy following focal		
	therapy (treated and untreated side).		
	Rates of second or third focal therapy sessions, in-field or out-of-field Pates of radiath graphs as adjusted as a shape therapy following surrant as		
	 Rates of radiotherapy as adjuvant or salvage therapy following surgery or focal therapy. 		
	Rates of prostatectomy as adjuvant or salvage therapy following		
	radiotherapy or focal therapy.		
	Rates of systemic therapy as adjuvant or salvage therapy following		
	surgery, radiotherapy or focal therapy. • Rates of prostate cancer-specific mortality.		
	Rates of all-cause mortality.		
	Long-term health outcomes of those participants consenting to longitudinal		
	follow-up will be reported in subsequent studies pending further funding.		
	Adverse events and functional outcomes		
	Rates of cystoscopic interventions following treatment.		
	Rates of implant insertion for treatment of incontinence and erectile dysfunction		
	dysfunction.Rates of medication and/or pump devices used for erectile dysfunction		
	following treatment.		
	Rates of endoscopic investigations of the lower bowel following treatment.		
	Rates of pad-use and quantity per day for urinary incontinence following		
	treatment. • Rates of pad-use and quantity per day for faecal incontinence following		
	treatment.		
	Rates of adverse event rates and complications.		

	Short Title: IP4 - CHRONOS	Protocol No: 19CX5006	Sponsor: Imperial College London	Version: 5.0 Date: 13 th July 2022
١				10 Gary Lore

 Genito-urinary and rectal side-effects using patient-reported outcome measures using validated questionnaires (EQ-5D-5L, International Index of Erectile Function-15, EPIC-26, EPIC Urinary domain, International Prostate Symptom Score and CTCAEv4.0 bowel domain) including evaluation of return to baseline function for erectile and urinary function and various minimum decreases in PROMS scores as defined for IIEF and IPSS in the literature that might be clinically relevant.

Health economics

- To establish the NHS costs of the different interventions.
- To determine the incremental cost per quality adjusted life year (QALYs) gained over the estimated lifetime of participants for focal therapy versus radical therapy.
- To determine the incremental cost per quality adjusted life year (QALYs) gained over the estimated lifetime of participants for focal therapy versus focal therapy with neoadjuvant and/or adjuvant strategies.

Qualitative

- The impact on participants' overall health-related quality-of-life including adverse events and impact on genito-urinary and rectal functional status using validated patient reported outcome measures.
- Descriptive analyses of the questionnaire data, and use of questionnaire and qualitative interview datasets in a multi-methods analysis to look for overarching themes in barriers and facilitators to participation in CHRONOS-A and CHRONOS-B.

Translational, Biobank and Databank

- Analysis on the localisation and nature of cancer-infiltrating immune cells and the immune-relevant gene expression within the cancer tissue.
- The creation of a biobank and databank of matched blood, serum, plasma and pre-digital rectal examination urine as well as imaging as well as FFPE biopsy samples.

Protocol No: 19CX5006 v5.0 13th July 2022

Short Title: IP4 - CHRONOS	Protocol No: 19CX5006	Sponsor: Imperial College London	Version: 5.0 Date: 13 th July 2022
			10 Gary 2022

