2.2 Main Study Primary Objectives

CHRONOS-A

To evaluate progression-free survival (PFS) rates of focal therapy alone compared to radical therapy (radiotherapy or surgery) in the treatment of non-metastatic clinically significant prostate cancer. PFS is defined as time from randomisation to salvage whole-gland or systemic therapy, prostate cancer metastases or prostate cancer-specific mortality.

CHRONOS-B

Short Title: IP4 - CHRONOS	Protocol No: 19CX5006	Sponsor: Imperial College London	Version: 5.0 Date: 13 th July 2022
			-

• To evaluate Failure-Free-Survival (FFS) rates of focal therapy alone compared to focal therapy combined with other therapies as a neoadjuvant strategy. FFS is defined as time from randomisation to further focal therapy session or salvage whole-gland or systemic therapy or prostate cancer metastases or prostate cancer-specific mortality.

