2.5 Main Study Primary Endpoints

CHRONOS-A

Progression-Free Survival (PFS) with progression defined as biochemical failure (radical therapies only), salvage therapy (local or systemic) or prostate cancer metastases or prostate cancer specific mortality. Salvage local therapy following focal therapy will be defined as surgery or radiotherapy or 3 or more focal therapy sessions. Any radiotherapy given after prostatectomy will be counted as an event.

CHRONOS-B

Failure-Free survival (FFS) with failure defined as time to one further focal therapy session or salvage therapy (local radiotherapy or surgery, or systemic) or prostate cancer metastases or prostate cancer specific mortality.

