2.6 Main Study Secondary Endpoints

Disease control

- Rates of positive biopsy for any cancer and significant cancer defined by a number of different thresholds on biopsy following focal therapy (treated and untreated side).
- Rates of second or third focal therapy sessions, in-field or out-of-field.
- Rates of radiotherapy as adjuvant or salvage therapy following surgery or focal therapy.
- Rates of prostatectomy as adjuvant or salvage therapy following radiotherapy or focal therapy.
- Rates of systemic therapy as adjuvant or salvage therapy following surgery, radiotherapy or focal therapy.
- Rates of prostate cancer-specific mortality.

IP4 - CHRONOS 19CX5006 Imperial College London Date: 13th July 2022	Short Title: IP4 - CHRONOS	Protocol No: 19CX5006	Sponsor: Imperial College London	
---	-------------------------------	--------------------------	-------------------------------------	--

- Rates of all cause mortality.
- Long-term health outcomes of those participants consenting to longitudinal follow-up will be reported in subsequent studies pending further funding.

Adverse events and functional outcomes

- Rates of cystoscopic interventions following treatment.
- Rates of implant insertion for treatment of incontinence and erectile dysfunction.
- Rates of medication and/or pump devices used for erectile dysfunction following treatment.
- Rates of endoscopic investigations of the lower bowel following treatment.
- Rates of pad-use and quantity per day for urinary incontinence following treatment.
- Rates of pad-use and quantity per day for faecal incontinence following treatment.
- Rates of adverse event rates and complications.
- Genito-urinary & rectal side-effects using patient-reported outcome measures using validated questionnaires (EQ-5D-5L, International Index of Erectile Function-15, EPIC-26, EPIC Urinary domain, International Prostate Symptom Score and CTCAEv4.0 bowel domain) including evaluation of return to baseline function for erectile and urinary function and various minimum decreases in PROMS scores as defined for IIEF and IPSS in the literature that might be clinically relevant.

Health economics

- To establish the NHS costs of the different interventions.
- The incremental cost per quality adjusted life year (QALYs) gained over the estimated lifetime of participants for focal therapy versus radical therapy.

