- As there is no defined time-point for a PSA nadir value following FT the PSA value at 12-months post randomisation in patients with a negative MRI will be used. Following this if there are any two further consecutive rises in PSA at least 3 months apart, with no influencing factors at the time (e.g., urinary tract infection, instrumentation/procedures, biopsies, catheterisation), a for-cause mpMRI with or without biopsies can be carried out at the discretion of the treating clinician. The Focal Therapy Sub-Group should be informed of this and a review of the for-cause mpMRI findings prior to biopsy should be carried out. Clinically significant prostate cancer in-field that is suitable for further FT should be offered to patients as a routine. Radical therapy should be only recommended to patients in instances where further FT is not suitable. Such situations should only occur after the Focal Therapy Subgroup has reviewed the case as expertise for such decisions may not reside in the local centre.
- In CHRONOS A, a second treatment either in-field or out-of-field will not be classified as failure and is part of the overall focal therapy intervention. In patients who undergo a second treatment of FT the nadir value will be defined at the 12-month time point after the second treatment, provided mpMRI and biopsy targeted at treated area(s) are negative for clinically significant prostate cancer.

Radiotherapy/ Brachytherapy

 In patients where there is suspected PSA relapse but the international definition of biochemical failure (PSA nadir plus 2.0ng/ml) has not been reached, evaluation should include a for-cause mpMRI and biopsy if required. Staging scans should be done as

Short Title: IP4 - CHRONOS	Protocol No: 19CX5006	Sponsor: Imperial College London	Version: 5.0 Date: 13 th July 2022
			10 daily 2022

per local practice. Where salvage local or systemic therapy is given, this will be regarded as PFS event.

Surgery

- Adjuvant or salvage radiotherapy will be regarded as a PFS event and will be determined based on histological findings and PSA kinetics even if the biochemical failure definition is not reached (PSA >/=0.2ng/ml). Staging scans should be done as per local practice.
- Biochemical failure following radical therapy as internationally defined, even if salvage therapy is not given, will be counted as an event for PFS/FFS analyses.

Collection of postcodes

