IP4 - CHRONOS 19CX5006 Imperial College London Date: 13 th July 2022	Short Title: IP4 - CHRONOS	Protocol No: 19CX5006	Sponsor: Imperial College London	
---	-------------------------------	--------------------------	-------------------------------------	--

Biochemical Failure

For the purposes of this trial, biochemical failure will be defined after surgery and radiotherapy/ brachytherapy as per standard care. Early adjuvant or salvage therapy can be given prior to biochemical failure if clinically determined through an MDT. These will count as events for purposes of PFS. Focal therapy does not have a validated definition for biochemical failure.

- Radiotherapy/ brachytherapy: PSA nadir plus 2ng/ml as per Phoenix definition
- Surgery PSA >/=0.2ng/ml at any time-point after surgery

Confirming biochemical failure

The timing and thus assessment of PSA needs to be considered because rises in PSA can occur due to non-cancer related causes such as after procedures, biopsies or urinary tract infection (UTIs). Confirmatory samples are needed in all cases of a rising PSA prior to assigning an outcome of biochemical failure. After biochemical failure is confirmed for the first time it need not be reported again.

In the case that the raised PSA value reaches the biochemical failure value, a second confirmatory PSA test should be performed after at least 1 week or after 4 weeks after the completion of treatment in cases of UTIs, procedures or biopsies. Biochemical failure is confirmed if the second value also confirms this. The date of biochemical failure should be provided as the date of the **first PSA** that fulfilled the definition for failure.

If salvage treatment does start before the trial definition of biochemical failure is met then report the closest PSA value prior to the treatment start date as the progression value.

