Based on an allocation ratio of 1:1 and a non-inferiority margin of 0.05 with a 0.85 PFS rate in the standard care arm (at median 5-years), power 0.80 and alpha 0.05, drop-out after randomisation of 5%, the overall required sample size is 1190 with 136 expected total number of events. Total recruitment and follow-up period will be 8 years. If recruitment rates were deemed to be high then the power could be adjusted to 0.90 and the total sample size will be 1660 with 189 expected total number of events. This will be on the advisement of the TSC. PFS for the main Stage will be defined as transition to salvage therapies or metastases or mortality related to prostate cancer.

CHRONOS-B main stages II and III: Using the latest update of –nstage-, with an allocation ratio of 1:1:1, we anticipate approximately 1200 patients are required over 5 years to observe 120 control arm failure-free survival (FFS) events within 7.6 years. This time will be dependent on observed FFS event rates and is based on an assumption of 20 patients recruited per month. This calculation gives 85% power at the efficacy stage analysis, to detect a hazard ratio (HR) of 0.67 and is based on 20% of patients having a FFS event by 3 years (30% by 5-years).

Table 1. Sample size calculations

	Short Title: IP4 - CHRONOS	Protocol No: 19CX5006	Sponsor: Imperial College London	Version: 5.0 Date: 13 th July 2022
١				10 Gary Lore

	Stage 1	Stage 2	Overall
Alpha	0.45	0.025	0.044
Power	95%	85%	83%
Critical HR (guidance for stopping early)	0.974		-
Control Arm Events	47	120	-
Accrual	20pts/m	20pts/m	20pts/m
Cumulative Patients	1003	1200	-
Time to analysis (years)	3.4	4.2	7.6

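### The CHRONOS-A primary endpoint (PFS) is defined inconsistently: sections differ on whether biochemical failure and adjuvant treatment are events, and counting them makes non-inferiority easier to show

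*Protocol*

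**What the plan says.** Five places in the protocol describe the CHRONOS-A PFS event.

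- **Trial Summary, Primary Endpoints:** biochemical failure ("radical therapies only) or salvage therapy (local or systemic) or prostate cancer" metastases or prostate cancer death). Adjuvant treatment is not named.
- **Section 2.2:** "PFS is defined as time from randomisation to salvage whole-gland or systemic therapy, prostate cancer metastases or prostate cancer-specific mortality". Neither biochemical failure nor adjuvant treatment appears.
- **Section 2.5:** opens with nearly the Summary's list and then adds "Any radiotherapy given after prostatectomy will be counted as an event".
- **Section 5.9:** under Surgery, "Adjuvant or salvage radiotherapy will be regarded as a PFS event", decided on histology and PSA kinetics, even below the biochemical failure threshold. Biochemical failure after radical therapy counts even when no salvage is given. Under Biochemical Failure, "Early adjuvant or salvage therapy can be given prior to biochemical failure if clinically determined through an MDT", and the next sentence makes these PFS events.
- **Section 8.1.2:** "PFS for the main Stage will be defined as transition to salvage therapies or metastases or mortality related to prostate cancer". Neither biochemical failure nor adjuvant treatment appears. This section also sets the 85% control PFS and the 5-point margin. It defends PFS as an endpoint measured identically in both arms, as time to salvage.

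In the focal arm, 5.9 makes a second focal session part of the intervention. Section 2.5 counts surgery, radiotherapy or a third focal session as salvage. The SAP covers the feasibility stage only and contains no PFS event definition, so it does not settle the matter.

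**The concern.** Take a control-arm man who has a prostatectomy, receives adjuvant radiotherapy on his pathology, and never recurs. He is an event under 2.5 and 5.9, and no listed event under the Summary, 2.2 or 8.1.2 applies to him. A man with biochemical failure and no further treatment is an event under the Summary, 2.5 and 5.9, but not under the wording of 2.2 or 8.1.2.

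Both kinds of event arise mainly after radical therapy. Biochemical failure is restricted to that arm by definition, because 5.9 notes that focal therapy has no validated equivalent. Extra control-arm events lower control PFS and move the comparison in favour of focal therapy, which in a non-inferiority trial is the direction that makes a false claim easier. Counting them also departs from the reason 8.1.2 gives for choosing PFS. And because the trial is open-label, an unsettled rule could end up being chosen when outcomes are already known.

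**Working it through.** **1. The definitions side by side**

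| Place | Biochemical failure (radical arm) | Adjuvant treatment | Salvage treatment |
|---|---|---|---|
| Trial Summary | event | not named | event |
| 2.2 | not named | not named | event |
| 2.5 | event | any radiotherapy after prostatectomy | event |
| 5.9 | event | radiotherapy after surgery; early adjuvant therapy before biochemical failure | event |
| 8.1.2 | not named | not named | event |

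Reading salvage as silently covering adjuvant is difficult, because the protocol uses the two words as alternatives elsewhere, for example in 2.6: "Rates of radiotherapy as adjuvant or salvage therapy following surgery or focal therapy".

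**2. The plan's own figures**

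Section 8.1.2 gives control PFS 0.85, margin 0.05, power 0.80, alpha 0.05 (sidedness not stated), 5% drop-out, 1190 patients and 136 events. The margin as a hazard ratio is ln(0.80)/ln(0.85) = 1.373. Freedman's formula at one-sided 0.05 gives

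(1.645 + 0.842)² × [(1.373 + 1)/(1.373 − 1)]² ≈ 251 events,

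and Schoenfeld's gives 247. The stated 136 is not reproduced from 0.85 and 0.80. It does match 0.90 against 0.85 (HR 1.5425, Freedman, one-sided 0.05). That is a separate matter and nothing below depends on it.

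**3. Illustration of size**

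Inputs from 8.1.2: evaluable men per arm n = 1190 × 0.95 / 2 ≈ 565; control PFS 0.85; focal PFS at the margin, 0.80.

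Assumption, not in the documents: a share q of control men has adjuvant treatment as the only PFS event within 5 years, with no matching extra events in the focal arm. The documents give neither the prostatectomy share nor an adjuvant rate. For scale, if none of these men would otherwise have failed, 50% surgery × 2% adjuvant gives q = 1%, and 30% × 10% gives q = 3%.

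With pc = 0.85 − q and pf = 0.80:

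SE = √[pc(1 − pc)/n + pf(1 − pf)/n]

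P(non-inferiority claimed) = Φ[(0.05 − (pc − pf))/SE − z]

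Worked at q = 1%: pc = 0.84; SE = √[(0.1344 + 0.16)/565] = 0.0228; (0.05 − 0.04)/0.0228 − 1.645 = −1.21; Φ = 11.4%.

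| q (about n of 565) | one-sided 5% | one-sided 2.5% |
|---|---|---|
| 0 | 5.0% | 2.5% |
| 1% (6) | 11.4% | 6.4% |
| 2% (11) | 21.8% | 13.7% |
| 3% (17) | 36.0% | 25.0% |

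**4. Check on the hazard-ratio scale**

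The planned analysis is a Cox model, so the calculation was repeated as Φ[(ln 1.373 − ln HR) × √(136/4) − 1.645], with HR = ln(0.80)/ln(pc). At q = 1%, 2% and 3% the HR is 1.280, 1.198 and 1.124, and the false-claim rate is 10.8%, 19.8% and 31.6%. The picture is the same.

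The same arithmetic applies to any control-only event, including biochemical failure never followed by another PFS event. Only men who would not otherwise have an event by 5 years contribute.

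**The case against.** The best reply is that silence is not contradiction. Every section that mentions adjuvant treatment counts it, and none says it is a non-event. Section 2.5 starts from almost the Summary's wording and adds detail, so the Summary can be read as its short form. This has force for the Summary. It is weaker for 2.2 and 8.1.2, which are phrased as definitions and also leave out biochemical failure, which the other sections count explicitly.

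Second, counting adjuvant treatment is defensible. Section 5.9 refers to PSA kinetics as well as histology, so some of this radiotherapy may reflect persistent disease. Counting all radiotherapy after prostatectomy also avoids an adjuvant-or-salvage label assigned in an open-label trial. That stands: the choice is legitimate either way, provided it is made once.

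Third, a reader might infer that the focal arm has no counterpart. It has partial ones. Section 2.5 counts any surgery or radiotherapy after focal therapy, and 5.8 treats hemiablation of the second lobe after a first hemiablation as failure.

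Fourth, the inflation presupposes that salvage-only is the intended endpoint. If the 85% already includes adjuvant events, the modelled fall in control PFS disappears. That also stands, and 8.1.2 does not say how the 85% was counted.

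**Conclusion.** The inconsistency in the primary endpoint is real, and the SAP does not resolve it. Its direction is clear: counting control-arm adjuvant treatment or biochemical failure favours a finding of non-inferiority.

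Its size is not known from the documents. On a salvage-only definition with focal therapy at the margin, adjuvant-only events in an assumed 1% to 3% of control men take a nominal one-sided 5% error to about 11% to 36%. If the 85% and the margin already include such events, there is no inflation.

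Stronger readings are tempting but not supported. Section 8.1.2 contains no rule excluding adjuvant therapy given without recurrence; it simply does not mention it. Higher assumed adjuvant rates would give larger errors, but nothing in the documents supports them. That planned hormones after radiotherapy would count is only one reading of 5.9. The documents also do not establish which rule is correct, or that non-inferiority has to hold under both.

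This should be fixed before the main stage. It does not affect the feasibility analyses, which do not use PFS.

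**What to change.** - State one PFS event definition that says explicitly whether biochemical failure and adjuvant treatment are events. Use it word for word in the Trial Summary, 2.2, 2.5, 5.9 and 8.1.2.
- State in 8.1.2 that the 85% control rate and the 5-point margin refer to that definition, or revise them so that they do.
- Record on the CRF whether treatment after radical therapy was given with or without evidence of recurrence. The secondary endpoints in 2.6 pool adjuvant and salvage treatment, so they do not guarantee that this is captured. Pilot patients carry over into the main stage (8.1.1), so the item is best added early.
- Pre-specify a sensitivity analysis of non-inferiority with adjuvant-only events handled the other way.

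The cost is protocol wording, one CRF item and one extra model fit. The change concerns what is counted and does not alter how any patient is treated.
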